9.6.1 Statistical Methods for Efficacy Analyses

This section describes the statistical methods that address the primary and secondary objectives. Methods related to exploratory objectives will be described in the sSAP.

There will be 2 estimands for the analysis of continuous efficacy endpoints, TP and TE. The primary hypothesis will be tested using both estimands. Based on local regulatory requirements, one of the estimands will be considered primary and the other supplementary. The key secondary endpoints and hypotheses associated with them (H2 and H3) will be analyzed under only the TP estimand.

The TP estimand consists of the following elements:

- Target population: Pediatric patients (age 10 to 17 years, inclusive) with T2DM who meet the glycemic criteria defined in this protocol
- Variable: Change from baseline in A1C at Week 24
- Intercurrent events: Regardless of whether study treatment or rescue medication was taken
- Population level-summary: Difference in means at Week 24
- Treatment Comparison of Interest: The effect of being randomized to ertugliflozin (combined doses) versus placebo.

Analyses corresponding to the TP estimand will include all available data at the Week 24 timepoint, including data after rescue or after the last dose of study treatment in any participants who remain in the study after discontinuing study treatment.

Analyses corresponding to the TP estimand will include all available data at the Week 24 timepoint, including data after rescue or after the last dose of study treatment in any participants who remain in the study after discontinuing study treatment.

The TE estimand consists of the following elements:

- Target population: Pediatric patients (age 10 to 17 years, inclusive) with T2DM who meet the glycemic criteria defined in this protocol
- Variable: Change from baseline in A1C at Week 24 as if all participants remained on treatment
- Intercurrent events: Data obtained after discontinuation of treatment or after taking rescue treatment are not relevant to this estimand
- Population level-summary: Difference in means at Week 24
- Treatment comparison of interest: The effect of taking the randomized treatments (ertugliflozin [combined doses] versus placebo).

The TE estimand will exclude measurements collected more than 5 days after the last dose of study treatment or after other AHA treatments, such as rescue/intensification treatment, are added.

For all efficacy analyses with the exception of exploratory analyses for participants who uptitrated from ertugliflozin 5 mg/day to 15 mg/day, participants will be classified as belonging to the ertugliflozin or placebo group according to their randomized treatment assignment at

Visit 3/Day 1/Randomization regardless of the treatment received during the course of the study.

Any participant randomized at the first or second randomization within the incorrect stratum will be classified according to the intended stratum in all analyses that include stratum. The intended stratum will be derived based on the participant's age and insulin use at Screening Visit/Visit 1 or insulin use at Visit 5/Week 12 as captured in the study database. An accounting of any incorrectly stratified participants will be provided in the CSR.

Week 24

For the primary analysis using the TP estimand, treatment group comparisons for the A1C mean change from baseline at Week 24 will be done using a Bayesian borrowing approach. The Bayesian borrowing approach will be done using an ANCOVA model with treatment, the age and insulin use strata as fixed effects, and the baseline A1C measurement as a covariate with normal priors on the model parameters and a mixture prior distribution on the treatment model effect, δ_p :

$$Y_{\text{Week24}} \sim N(\beta_0 + \beta_1 * \text{Age} + \beta_2 * \text{Insulin Use} + \beta_3 * \text{Baseline A1C} + \delta_p * \text{Treatment}, \sigma^2).$$

The model parameters for intercept, age, insulin use and baseline A1C will have wide normal prior distributions as follows:

$$\beta_i \sim N(0, 100^2), i = 0,1,2,3$$

The treatment effect parameter will have a mixture normal prior with 2 components: an informative prior mean and variance based on the full ITT population from the 8835-007 study and a general skeptical prior. The prior distribution of δ_p is as follows:

$$\delta_p | z = 0 \sim N_{general} (0, (1.5*1.5^2))$$

$$\delta_p | z = 1 \sim N_{adult} (-0.598, 0.066^2)$$

where the weight z has a prior Bernoulli distribution with a parameter, p.

For the primary analysis, a Bernoulli parameter of 0.134 will be used. The skeptical prior variance as well as the mixture prior parameter of 0.134 were selected based on the Effective Sample Size (ESS) metric as defined in Neuenschwander et al. [Neuenschwander, B., et al 2020]. For the variance of the general normal distribution in the mixture prior, an ESS of 3 pediatric participants (2 in ertugliflozin arm and 1 in placebo arm) will be used to ensure the prior is skeptical without being non-informative. A prior parameter with a value of 0.134 was selected to ensure the mixture distribution has an ESS equal to a total of 165 pediatric participants (110 in ertugliflozin arm and 55 in placebo arm). This will ensure that the information borrowed from the mixture prior does not exceed the planned sample size of 165 pediatric participants in the P059 study.

[figure not shown]
The success criterion for declaring that ertugliflozin (pooled doses) is superior to placebo in reducing A1C at Week 24 is having the upper bound of the posterior 95% credible interval for $\delta_p < 0$.

As a sensitivity analysis, a tipping point-like approach will be used in which the prior weight parameter, p, will be varied from 0 to 1 in increments of 0.05. The point at which the analysis shifts from not significant to significant will be noted.

Data permitting (discussed below), missing data will be imputed using an RD approach which assumes that all missing Week 24 data can be represented by the observed Week 24 data for participants in the same group who discontinued study treatment but remained in the study.

A "retrieved dropout" value is defined as an observed Week 24 value in a participant who discontinued study medication prior to Week 24 but remained in the study. For the RD approach, missing Week 24 values will be imputed as follows:

[figure not shown]
RD imputation will be done within each treatment arm (placebo or combined ertugliflozin for H1, placebo or dose-optimized ertugliflozin for H2, or placebo or ertugliflozin 5 mg for H3). All Week 24 RD values will be used for imputation, regardless of when a participant discontinued from study medication.

PROTOCOL/AMENDMENT NO.: 059-04

The RD analysis may not be feasible due to insufficient observed Week 24 data post discontinuation of study medication. If the number of RD participants per group is at least 50% of participants who discontinue from study medication per arm, then RD will be the primary approach to impute missing data for the TP estimand. If at least one group has either less than 50% RD participants or fewer than 5 total RD participants, then RD will not be performed, and WI will become the primary analysis method. If the minimum data requirement for the RD method is met, then WI will be implemented as a sensitivity approach for the TP estimand. The WI analysis assumes participants who prematurely discontinued from the study or who have an intermittent missing Week 24 value would have a 'washout' of any potential effect of the assigned study medication.

For all analyses involving simulated data, a seed of 8835059 will be used for random number generation.

A constrained longitudinal data analysis (cLDA) model, based on Liang and Zeger [Liang, K.-Y. and Zeger, S. L. 2000], will be used for analyses addressing the TE estimand for A1C mean change from baseline and FPG mean change from baseline. Time will be treated as a categorical variable so that no restriction is imposed on the trajectory of the means over time. The cLDA model will also adjust for treatment, the age stratum, the insulin use stratum, and the interaction of time by treatment. The cLDA model assumes a common mean across treatment groups at baseline within each age and insulin use category (due to randomization) but different means between categories, and a different mean for each treatment at each of the post-baseline timepoints. In the cLDA model, the response vector consists of baseline and the values observed at each post-baseline timepoint. The treatment difference in terms of mean change from baseline to a given timepoint will be estimated and tested from this model. An unstructured covariance matrix will be used to model the correlation among repeated measurements.

For the cLDA model, the Kenward-Roger adjustment will be used with restricted (or residual) maximum likelihood (REML) to make proper statistical inference. An unstructured covariance matrix will be used to model the correlation among repeated measurements and hence avoids the potential bias that could result from the use of specific structured covariance models. If the unstructured covariance model fails to converge with the default Newton-Raphson algorithm, the Fisher scoring algorithm or other appropriate methods can be used to provide initial values of the covariance parameters. In the rare event that none of the above methods yield convergence, a structured covariance such as Toeplitz can be used to model the correlation among repeated measurements. In this case, the empirical option will be used because the sandwich variance estimator is asymptotically unbiased while the model-based variance estimator can substantially overestimate or underestimate the true variance. The cLDA model uses the maximum likelihood principle to estimate the parameters and account for missing data in an implicit fashion.

Although the baseline measurement is included in the response vector, it is independent of treatment, and hence, the baseline means are constrained to be the same for different treatment groups within the same age and insulin use categories. Of note, in the event that there are no missing data, the estimated treatment difference from the above cLDA model will be identical to that from a traditional longitudinal ANCOVA model, which uses the baseline value as a covariate. However, unlike longitudinal ANCOVA, the cLDA model accounts for variability in the baseline values, thus providing more accurate standard errors and CIs for individual treatment effects. Moreover, this model allows the inclusion of participants who are missing either the baseline or post-baseline measurements, thereby increasing efficiency.

The cLDA method assumes that the mechanism for missing data is missing at random (MAR).

Assessment of the Key Secondary Endpoints

The key secondary endpoints will be evaluated under only the TP estimand analysis approach.

PROTOCOL/AMENDMENT NO.: 059-04

All elements of the TP estimands below are the same as the primary TP estimand except for the treatment comparisons:

Treatment comparison of interest:

For H2 - The effect of being randomized to dose-optimized ertugliflozin versus placebo.

For H3 - The effect of being randomized to ertugliflozin 5 mg versus placebo.

Specific weighting schemes will be used to test H2 and H3. The weighting schemes are defined as follows:

- All participants on placebo have a weight of 1
- All participants on ertugliflozin who were not re-randomized at Visit 5/Week 12 have a weight of 1
- For H2 the hypothesis comparing dose-optimized ertugliflozin to placebo (weighting scheme A):
 - All participants on ertugliflozin who were re-randomized to 5 mg at Visit 5/Week 12 have a weight of 0
 - All participants on ertugliflozin who were re-randomized to 15 mg at Visit 5/Week 12 have a weight of 2
- For H3 the hypothesis comparing ertugliflozin 5 mg with placebo (weighting scheme B):
 - o Participants who were re-randomized to 5 mg at Visit 5/Week 12 have a weight of 2
 - Participants who were re-randomized to 15 mg at Visit 5/Week 12 have a weight of 0

For the key secondary endpoints, treatment group comparisons for the A1C mean change from baseline at Week 24 will be done using an ANCOVA model with treatment, the age and insulin use strata as fixed effects, and baseline measurement as a covariate. Hypotheses H2 and H3 analyses for RD and WI are shown below.

The RD imputation and analysis steps are as follows for H2 and H3 using Rubin's rule for 100 total imputed datasets:

- 1. Within each imputation sample, do the following:
 - a. Impute missing Week 24 values using a normal distribution where the expected change from baseline value is set to the estimated mean change from baseline value from the RD participants in the same treatment group. The standard deviation will be the RMSE derived from the ANCOVA model described above and estimated based on all participants with Week 24 data.
 - b. After step a, each of the 100 resulting datasets will contain the original non-missing data and the imputed data for those with missing Week 24 values.
- 2. The 100 datasets will be analyzed using a weighted ANCOVA model with Baseline A1C and the two stratification factors as covariates. The weights will be defined as listed above and included in the model using the weight option from SAS PROC MIXED. The 100 weighted ANCOVA-based estimates of the treatment difference will be combined using PROC MIANALYZE based on Rubin's rule, which accounts for between and within imputation variability.

The WI imputation and analysis steps are as follows for H2 and H3:

For participants in the ertugliflozin group:

- 1) Fit a regression model as $Y_{24} = \beta_0 + \beta_1 * Y_0 + \gamma * X + \text{error}$, where Y_0 and Y_{24} are the placebo group A1C values at Baseline and Week 24, respectively, and X is a matrix for the age and insulin stratum fixed covariates.
- 2) Impute missing Week 24 A1C values for ertugliflozin using the estimated mean from the above model and standard deviation equal to the RMSE from the model.

For participants in the placebo group:

- 1) Fit models according to the intermittent missing data pattern with A1C values from the placebo group only:
 - a. For participants with only Baseline data: $Y_{24} = \beta_0 + \beta_1 * Y_0 + \gamma * X + \text{error}$
 - b. For participants with only Baseline and Week 6 data: $Y_{24} = \beta_0 + \beta_1 * Y_0 + \beta_2 * Y_6 + \gamma * X + \text{error}$
 - c. For participants with only Baseline, Week 6 and Week 12 data: $Y_{24} = \beta_0 + \beta_1 * Y_0 + \beta_2 * Y_6 + \beta_2 * Y_{12} + \gamma * X + error$
- 2) Impute missing Week 24 A1C values for placebo using one of the 3 models above based on the missing data pattern with a mean equal to the mean from the regression model and a standard deviation equal to the RMSE from the model.

Descriptive statistics will be used to summarize the A1C mean change from baseline at Week 24 for the individual ertugliflozin dose arms in the subset of participants who were rerandomized at Visit 5/Week 12. All other continuous efficacy endpoints with the exception

of the 2 key secondary endpoints associated with hypotheses H2 and H3, including the Week 12 A1C change from baseline, will be analyzed following the same cLDA method used for the A1C TE estimand under H1 (combined ertugliflozin doses vs. placebo) and will not be analyzed under the TP estimand.

Week 54

The Week 54 analyses will be based on the same FAS population used for the Week 24 analyses. The statistical models for the analyses at Week 54 will be analogous to those at Week 24, except that no between-group comparisons will be provided for **Week 54**. The efficacy endpoints will be summarized for within-group mean change from baseline with estimates and 95% CIs calculated from the analysis model.

Table 7 summarizes the analysis strategy for primary and secondary efficacy endpoints at Week 24 and at Week 54.

Table 7 Analysis Strategy for Efficacy Variables at Week 24 and at Week 54

Variable	Estimand/Approach	Statistical Method	Missing Data Approach
Primary			
Change from baseline in	TP/Primary	Bayesian Borrowing	RD^\dagger
A1C - pooled ertugliflozin vs placebo	TE/Primary	cLDA	Model-based
Key Secondary			
Change from baseline in A1C - dose-optimized ertugliflozin vs placebo	TP/Primary	ANCOVA (weighting scheme A)	RD^\dagger
Change from baseline in A1C - ertugliflozin 5 mg vs placebo	TP/Primary	ANCOVA (weighting scheme B)	RD^\dagger
Secondary			
Change from baseline in FPG	TE/Primary	cLDA	Model-based

A1C = glycosylated hemoglobin; ANCOVA = analysis of covariance; cLDA = constrained longitudinal data analysis; FPG = fasting plasma glucose; RD = Retrieved Dropout; TE = Treatment Effect; TP = Treatment Policy; WI = Washout Imputation.

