Note: All participants on background insulin must have a fasting C-peptide value >0.6 ng/mL with a concurrent FPG >100 mg/dL (5.56 mmol/L) at Screening Visit/Visit 1 regardless of duration of T2DM. If FPG ≤100 mg/dL (5.56 mmol/L) C-peptide levels should be measured at an Unscheduled Visit/Visit 2/Week -1, at least 30 minutes, but no longer than 2 hours after a meal. Participants must have a C-peptide value >1.5 ng/mL in the post-meal period.

3. Be:

- i. On stable metformin monotherapy (≥1500 mg/day, for ≥8 weeks prior to **Screening Visit/Visit 1**), OR
- ii. On a stable metformin dose (≥1500 mg/day, for ≥8 weeks prior to **Screening Visit/Visit 1**) and a stable dose of insulin (of any type, variance in dose to be ≤15% of total daily dose for ≥8 weeks prior to **Screening Visit/ Visit 1**).

 Note: This stable dose can include: (1) a stable dose of basal insulin (±15%) AND/OR (2) stable prescribed doses of bolus insulin (±15%) (a) for each fingerstick glucose (FSG) range for participants on sliding scale OR, if applicable, (b) for corrective doses and carbohydrate coverage.

Notes:

- a. Participants on stable doses of metformin \geq 1000 and <1500 mg/day (\pm insulin) for \geq 8 weeks can participate if there is documentation that they cannot tolerate higher doses of metformin.
- b. Participants on metformin doses ≥1000 and <1500 mg/day (± insulin) can have their metformin doses up-titrated to ≥1500 mg/day and be eligible to participate after their dose remains stable for ≥8 weeks, if they meet eligibility criteria when they are rescreened. If up-titration of metformin is not tolerated, it must be documented, and the participant will be eligible if they meet all other **Screening Visit/Visit 1** eligibility criteria.
- c. At **Screening Visit/Visit 1**, participants on insulin doses that are not stable can have the insulin doses adjusted and be eligible to participate after their dose remains stable for ≥ 8 weeks, if they meet eligibility criteria when they are rescreened.
- 4. Have an A1C ≥6.5% and ≤10.0% (48 mmol/mol and 86 mmol/mol) at **Screening Visit/Visit 1** if on metformin monotherapy, OR an A1C ≥7.0% and ≤10.0% (53 mmol/mol and 86 mmol/mol) at **Screening Visit/Visit 1** if on metformin + insulin.

Demographics

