Statistical Methods for Key Efficacy/Immunogenicity/ Pharmacokinetic Analyses	The primary hypothesis will be evaluated by comparing ertugliflozin (combined 5 mg and 15 mg doses) to placebo with respect to A1C change from baseline at Week 24. The treatment policy (TP) estimand is expected to be considered primary in some regions. In all other regions, the Treatment Effect (TE) estimand will be primary. The TP estimand will estimate the difference in change from baseline means comparing the effect of being randomized to ertugliflozin versus placebo whereas the TE estimand will estimate the effect of being treated with ertugliflozin versus placebo. The primary analysis approach for the TP estimand will evaluate the treatment difference via a Bayesian borrowing approach using an informative prior distribution derived from a completed adult study of ertugliflozin (MK-8835 P007) and with missing Week 24 A1C data imputed using a Retrieved Dropout (RD) or Washout Imputation (WI) approach. The weight given to the adult prior distribution for the primary hypothesis test will be 0.134. The primary analysis approach for the TE estimand will evaluate the treatment difference via a frequentist analysis using a constrained longitudinal analysis model (cLDA). The key secondary hypotheses will be assessed using an ANCOVA model after imputing missing data using RD or WI. These hypotheses will be tested under only the TP estimand and will apply weights to the treatments as follows: • Participants on ertugliflozin 5 mg who were not re-randomized at Visit 5/Week 12 have a weight of 1 For the hypothesis comparing the addition of ertugliflozin, with dosing optimized according to A1C response, to the addition of placebo, the weights for the re-randomized participants will be defined as follows: • Participants who were re-randomized to 15 mg at Visit 5/Week 12 have a weight of 2		

C Confidential

	 Participants who were re-randomized to 5 mg at Visit 5/Week 12 have a weight of 0. For the hypothesis comparing ertugliflozin 5 mg with placebo the weights for the re-randomized participants will be defined as follows: Participants who were re-randomized to 5 mg at Visit 5/Week 12 have a weight of 2. Participants who were re-randomized to 15 mg at Visit 5/Week 12 have a weight of 0. 	

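### The TE cLDA model holds the age and insulin stratum effects constant over time, so its claimed equality with ANCOVA is false as written; the numerical effect is small

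*Combined protocol and SAP*

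**What the plan says.** Section 9.1 makes the TP estimand primary in some regions and adds: "In all other regions, the Treatment Effect (TE) estimand will be primary". The TE analysis is the cLDA of Section 9.6.1. Table 7 uses the same model for FPG, and the section extends it to the other continuous efficacy endpoints apart from the two key secondary ones.

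The model is described in three places in Section 9.6.1:

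- Terms, with time categorical: "The cLDA model will also adjust for treatment, the age stratum, the insulin use stratum, and the interaction of time by treatment".
- Outcome: "the response vector consists of baseline and the values observed at each post-baseline timepoint".
- Means: arms share a baseline mean within each age and insulin category, "but different means between categories, and a different mean for each treatment at each of the post-baseline timepoints".

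The section then says that, with no missing data, "the estimated treatment difference from the above cLDA model will be identical to that from a traditional longitudinal ANCOVA model", the comparator being one with baseline as a covariate.

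The TP analysis is an "ANCOVA model with treatment, the age and insulin use strata as fixed effects, and the baseline A1C measurement as a covariate", fitted to the Week 24 value. The key secondary ANCOVAs have the same covariates.

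Data after rescue are excluded under TE, and the cLDA relies on missingness at random.

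**The concern.** Time-by-treatment is the only interaction named. Read as written, each stratum has one effect shared by baseline and Weeks 6, 12 and 24. The model then assumes that insulin users and non-users, and younger and older participants, follow parallel A1C courses. The TP model makes no such assumption, so two analyses that are each primary somewhere treat the randomization strata differently.

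Three things follow if the strata are not parallel:

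- The difference between strata in change goes into the residual variance, although stratified randomization has already balanced it.
- Likelihood estimation under missingness at random protects the estimate only if the mean model is right. A wrong Week 24 stratum gap can therefore matter when censoring is unbalanced.
- The sentence on equality with ANCOVA, which supports the choice of a primary method, does not describe the model specified.

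**Working it through.** **1. The plan's own power figure.** Section 9.9 gives 95 and 47 evaluable, a difference of -0.75 and an SD of 1.5. No alpha is stated for the TE test, so two-sided 0.05 is assumed. SE = 1.5 × √(1/95 + 1/47) = 0.2675; 0.75/0.2675 = 2.804; Φ(2.804 - 1.960) = 80.1%. With the Section 9.9 covariance matrix, 4/8/14% attrition and 110/55 participants, the SE is 0.264 and power 81.0%. The stated figure of at least 80% is reproduced.

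**2. Structure.** Let g be a constant stratum effect, b the slope of Week 24 on baseline, μ the visit means and δ the Week 24 treatment effect.

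- Mean change: (μ24 + g + δ) - (μ0 + g) = μ24 - μ0 + δ. The stratum effect cancels.
- Given baseline, the Week 24 stratum coefficient is g - b·g = g(1 - b). It is not zero, but it is tied to the constant effect.
- If strata differ in Week 24 change by τ, the coefficient that ANCOVA estimates freely is g(1 - b) + τ. The cLDA as written has no parameter for τ.

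**3. Simulation inputs.** From Section 9.9: N = 165 at 2:1, the conditional covariance matrix and the effect of -0.75; overall attrition of 14% is used where censoring is equal across cells. Assumed, because the documents give no values: baseline variance 0.9; slopes on baseline 0.9/0.8/0.7; 40% on insulin; insulin users 0.5 points higher at baseline; τ (insulin stratum) from 0 to 1.0. Both models were fitted to the same data by maximum likelihood with unstructured covariance. The plan specifies REML with Kenward-Roger, so small-sample values are approximate.

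**4. Equality with ANCOVA** (complete data, N = 165, 300 datasets per τ; largest absolute difference in the Week 24 estimate):

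| τ | As written vs ANCOVA with strata | As written vs ANCOVA without strata | Strata crossed with time vs ANCOVA with strata |
|---|---|---|---|
| 0 | 0.012 | 0.033 | below 0.00000001 |
| 0.5 | 0.021 | 0.077 | below 0.00000001 |
| 1.0 | 0.039 | 0.124 | below 0.00000001 |

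The SE is about 0.25, so these are small differences, but they are not zero even when τ = 0.

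**5. Standard error and power** (14% missing in every cell; large-sample fit scaled to N = 165; power = Φ(0.75/SE - 1.960)):

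| τ | SE as written | SE crossed | Ratio | Power as written | Power crossed |
|---|---|---|---|---|---|
| 0 | 0.2630 | 0.2630 | 1.000 | 81.4% | 81.4% |
| 0.3 | 0.2651 | 0.2640 | 1.004 | 80.8% | 81.1% |
| 0.5 | 0.2684 | 0.2653 | 1.012 | 79.8% | 80.7% |
| 1.0 | 0.2756 | 0.2632 | 1.047 | 77.7% | 81.3% |

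The actual sampling SD at N = 165 barely differs: 0.2643 against 0.2645 at τ = 0.5, and 0.2653 against 0.2629 at τ = 1.0. The cost is mainly an overstated SE.

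**6. Bias.** The large-sample fits used 60,000 participants, so each single estimate has a Monte Carlo error of about 0.263 × √(165/60,000) = 0.014. The difference between the models on the same data is the useful quantity.

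- Censoring 23% in insulin users and 8% in others, equal in both arms: the models agree within 0.001.
- Censoring 45% in placebo insulin users and 9-10% in the other cells: as written minus crossed is 0.030 - 0.008 = 0.022 (τ = 0.3), 0.014 + 0.019 = 0.033 (τ = 0.5) and 0.077 - 0.012 = 0.065 (τ = 1.0), towards zero.
- The same pattern at N = 165, 1,500 datasets: 0.045 - 0.009 = 0.036 (τ = 0.5) and 0.075 - 0.008 = 0.067 (τ = 1.0). Power is 73.5% against 77.5%, and 67.5% against 78.3%; part of each gap is the larger SE.

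**7. A second set of assumptions** (half on insulin, baseline gap 0.6, baseline SD 0.9, slopes 0.80/0.75/0.65). SE ratio 1.010-1.012 at 0.5 and 1.043-1.048 at 1.0. Power 79.3% with parallel strata, 78.6% at 0.5 and 76.0% at 1.0. With censoring of 36%/12% on placebo (insulin/no insulin) and 12%/6% on ertugliflozin, the shift is 0.017 at 0.5 and 0.037 at 1.0.

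**The case against.** The list of terms may be loose prose rather than a model statement. It names a treatment effect, although the baseline means are constrained to be equal across arms, and the section also says that treating time as categorical leaves the mean trajectories unrestricted. The ANCOVA sentence is an aside that governs no analysis step, and it does not say which strata terms the comparator contains. This has force: incomplete wording is a fair description. But one interaction is named and the others are not, so a programmer following the text would omit them, and the equality fails against ANCOVA with or without strata.

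Nothing in the documents shows that the strata differ in their change. The entry limits do not: insulin users need a higher A1C ("if on metformin monotherapy, OR an A1C ≥7.0% and ≤10.0"), against a floor of 6.5% on metformin alone, but that implies a gap at baseline, which the model allows. A τ of 1.0 would exceed the assumed treatment effect of 0.75. Both points stand, so the larger figures are the outer end of a range.

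A reader might infer that the strata are not adjusted for at all. That goes too far, because the constrained coefficient g(1 - b) remains. Nor does bias follow whenever rescue differs by stratum: when it differed by stratum alone, the two models agreed.

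Finally, Section 9 requires a protocol amendment for a change to a primary method, and Section 9.9 says that all participants have completed or left Phase A. The change is therefore late and more than an editorial correction.

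**Conclusion.** The point holds as a minor specification fault. As written, the TE cLDA constrains the Week 24 stratum gaps to equal the baseline gaps, and the equality statement is untrue for that model, by about 0.01 to 0.04 at most against stratum-adjusted ANCOVA.

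The other effects are conditional. If strata differ in A1C change, the reported SE is about 1% too large at 0.5 points and 4-5% at 1.0, or roughly 1 and 3-4 power points. If, in addition, censoring differs by both stratum and arm, the estimate shifts by about 0.02-0.04 and 0.04-0.07. The shift was towards zero in the cases in step 6; its direction depends on the sign of the stratum difference. These sizes rest on assumed insulin share, baseline gap and variance, slopes, stratum difference and censoring pattern. With parallel strata there is no systematic cost.

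A reader might also infer that the planned power is wrong or that type I error is inflated. The documents do not support the first, since the 80% reproduces. Nothing in the calculations points to the second: with equal censoring the SE is overstated, not understated.

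**What to change.** In Section 9.6.1, before unblinding, specify the cLDA mean model as time, age stratum by time, insulin stratum by time, and treatment by post-baseline time, with no treatment effect at baseline. Apply it to A1C and FPG. Reword the equality statement to name ANCOVA adjusted for the same strata; it is then correct, and the TE and TP analyses adjust for the strata on the same basis.

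The cost for A1C through Week 24 is 2 strata × 3 post-baseline visits = 6 mean parameters with 165 participants, plus inclusion in a protocol amendment. If the sponsor prefers to keep constant stratum effects, the minimum is to withdraw the equality statement and justify the assumption of parallel strata.
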